### 11.9 Adverse Event Outcome Classification

Outcome of the event will be defined according to the following:

- *Resolved:* The event has fully resolved at the end of the study.
- *Resolved with sequelae:* The event has resolved, but retained pathological conditions resulting from the prior disease or injury.
- *Continuing:* The event is ongoing at the end of the study.
- *Death:* This event is determined to be the cause of death.

### 11.10 Adverse Event Recording

Assessment of the occurrence of an AE will be based on changes in the subject's physical examination, laboratory results and/or signs and symptoms. Adverse events will be monitored from the start of the CCE/CTC bowel preparation and end with the OC follow up call

For purposes of the TOPAZ protocol, the following occurrences are considered to be expected observations following bowel preparation (vomiting, nausea, headache, dizziness, gagging, hemorrhoidal bleeding, bloating, rash, abdominal pain, syncope, tinnitus, chest burning, chills, and flu-like symptoms) and will not be considered reportable AEs, as long as the event is not defined as a SAE. Adverse Events should be reported to MDT study team within 10 working days.

The potential serious adverse events associated with the use of the device:

- include delayed or no excretion of the capsule, per IFU: Capsule retention is defined as having a capsule remain in the digestive tract for more than two weeks.
- aspiration,
- obstruction,
- perforation, and mucosal injury or bleeding.
- In some instance, intervention is required to remove the capsule.

The following should not be considered an AE:

- A condition requiring a preplanned procedure unless the condition worsened since screening
- A preexisting condition found as a result of screening, unless the condition has worsened since enrollment.

All responses to the above events that require treatment beyond the institution's standard procedures will be reported as AEs.

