## 8.0 Study Design

This is a multicenter, prospective, randomized study to evaluate the efficacy of CCE versus CTC in the identification of colonic polyps in a screening population.

Subjects will be enrolled at up to 20 clinical sites in the United States. Subjects who meet the eligibility criteria will be screened by the gastroenterology site for study participation at a baseline visit which will also include a blood test for renal function (eGFR), and will be evaluated on the randomized procedure day (CCE versus CTC) and again on the day of both the blinded and unblinded OC procedures.

Telephone follow-ups will be conducted 5 – 9 days after the CCE/CTC procedure and 5 – 9 days after the unblinded OC procedure to assess subject well-being and capture any AEs, regardless of relationship to the CCE, CTC, or OC procedures. On the second follow-up call after the OC procedure, subjects will be requested to answer procedure preference questions (sample questionnaires are included in Appendix D).

All CCE RAPID® videos and CTC images will be evaluated by local and central readers. All study analyses will be based on central reader results for both CCE and CTC. Two sets of central readers will be utilized, one set for reading of the CCE RAPID® videos and one set for reading the CTC studies. Both groups of readers will be experts in the reading process for their respective procedures. Readers will provide a report of their findings to the sponsor within 2 weeks of capsule ingestion or CTC procedure in order to allow subjects to return within 5 weeks capsule ingestion or CTC procedure to undergo confirmatory OC. The first OC procedure will be performed with the clinician blinded to the CCE or CTC results. Immediately following this blinded procedure, the clinician will review the CCE or CTC results report provided by the sponsor from the central readers, and a second unblinded OC procedure will be performed if there are discrepancies between the CCE/CTC findings and OC.

Colonoscopy must not be performed by the same person who conducts the local CCE reading, or anyone who has reviewed CCE/CTC results for that subject.

In cases of polyp size measurement discrepancies between CCE/CTC and OC, a Clinical Events Committee (CEC) will adjudicate OC polyp size measurements. Bowel preparation regimens for all three procedure types will be standardized across sites and are described in detail in the Appendix.

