**8.5 Safety Endpoints**

AEs will be reported by number, severity, timing, and relationship to the study procedures (imaging modality, colonoscopy), as described in Sections 11.7 and 11.8. The recording of adverse events for all

enrolled subjects will begin with the start of the CCE/CTC bowel preparation and end with the OC Follow-up call. All AEs will be captured, regardless of severity or relationship to the procedure.

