## 11.0 Adverse Events and Complications

Adverse events will be collected at the start of the CCE/CTC bowel preparation and end with the OC Follow-up call (5-9 days after the unblinded OC procedure). During the course of the study the following AEs and serious adverse events (SAEs) will be collected:

- All adverse events related to the CCE, CTC and or OC procedures
- All retained capsules greater than 14 days
- All perforations
- All device deficiencies that may lead to a SAE
- All adverse events that meet serious adverse event definition in Section 11.2
- All deaths

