### **11.3 Adverse Device Effect (ADE)**

An Adverse Device Effect (ADE) is an occurrence related to or caused by the investigational device, procedure or comparator that is not serious. This includes use error or intentional abnormal use of the device. In addition inadequacies in the instructions for use, the deployment, the implantation, the installation, the operation, or any malfunction of the device are also included.

In the case of an ADE, OC should be postponed until the ADE is resolved and per physician discretion.

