### 11.8 Adverse Event Relationship Classification

AE relationship to study procedures will be reported for 3 procedure types:

1. CCE (including capsule and/or sensors)
2. CTC Exam
3. Colonoscopy Exam

For each of the 3 procedure types above, relationship will be categorized as:

- *Not Related:* No relationship between the AE and the administration of any study procedure and a known relationship to other etiologies such as concomitant medications, non-study procedures, or the subject's clinical state.
- *Related:* An AE that follows a plausible temporal sequence from administration of a study procedure and follows a known response pattern to a study procedure. The reaction cannot be reasonably explained by the known characteristics of the subject's clinical state or other modes of therapy administered to the subject.
- *Impossible to Determine:* Given the information available, sequence and timing of events, it is impossible to determine the relationship of the AE with the study procedure.

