#### Investigator AE Reporting Requirements

Type	Report to	Reporting Timeframe (from time of learning of event)
Adverse Event (AE)	IRB/EC	Per IRB reporting requirements
	Sponsor	Within 10 working days
Serious Adverse Event (SAE)	Sponsor	Within 10 working days
	IRB/EC	Per IRB reporting requirements
Adverse Device Effect (ADE),	Sponsor	Within 10 working days
	IRB/EC	Per IRB reporting requirements

Serious Adverse Device Effect (SADE) and Unanticipated Serious Adverse Device Effect (USADE)		
Device Deficiency	Sponsor (technical support)	Within 10 working days
	IRB/EC	If SAE occurs due to the device deficiency, within 10 days and per IRB reporting requirements
Device Related AE/SAE	Sponsor	Within 10 days

All events will be reviewed by Medtronic safety officer or designee to determine any reporting obligations to the IRB.

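### Sections 8.5, 11.0, 11.1 and 11.10 give contradictory capture rules for non-serious AEs, and the 11.10 exemption as worded can drop symptoms caused by CCE, CTC or colonoscopy

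*Combined protocol and SAP*

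**What the plan says.** The rules for recording AEs are spread over several sections of the combined protocol and SAP.

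- **8.5 Safety Endpoints:** "All AEs will be captured, regardless of severity or relationship to the procedure". Recording is to "begin with the start of the CCE/CTC bowel preparation and end with the OC Follow-up call".
- **8.0 Study Design:** the two telephone follow-ups are to "capture any AEs, regardless of relationship to the CCE, CTC, or OC procedures".
- **11.1:** an AE is defined without regard to relationship, and AEs are collected until the follow-up call after colonoscopy.
- **11.0:** this section lists what will be collected. The first entry is "All adverse events related to the CCE, CTC and or OC procedures". The others are capsules retained longer than 14 days, perforations, device deficiencies that may lead to an SAE, SAEs and deaths.
- **11.3 and 11.11:** an ADE is an occurrence "related to or caused by the investigational device, procedure or comparator that is not serious". The 11.11 table gives ADEs a reporting deadline of 10 working days and has a further row headed "Device Related AE/SAE".
- **11.10:** 14 symptoms are described as expected after bowel preparation and "will not be considered reportable AEs, as long as the event is not defined as a SAE". The section closes by making responses reportable when they need treatment that goes past the institution's usual practice.
- **11.8:** "AE relationship to study procedures will be reported for 3 procedure types", namely CCE, CTC and colonoscopy. Each is graded Not Related, Related or Impossible to Determine. Bowel preparation is not among the three types.
- **9.4:** the arms are compared on the proportions with at least one AE, at least one SAE, at least one CCE/CTC-related AE and at least one colonoscopy-related AE.

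**The concern.** A site that sees a non-serious event has to decide whether to enter it, and the answer changes with the section it consults. Events that were never entered are hard to recover at analysis. Appendices A, B and C name the comparison of safety as a purpose of the study, and 9.4 tests AE proportions between arms, so the capture rule feeds directly into a planned comparison.

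The 11.10 exemption is the more serious part. It is triggered by the name of the symptom and by its coming after a preparation. It does not ask whether the preparation, the capsule, the CTC insufflation or the colonoscopy caused the symptom. If the two arms differ in how often a procedure causes one of the listed symptoms, a literal application removes different numbers of procedure-related events from each arm.

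**Working it through.** No AE rate, AE sample size or AE power is stated in the plan, so there is no figure to reproduce. The check is a side-by-side reading.

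**Step 1: count the exempt symptoms.** 11.10 names vomiting, nausea, headache, dizziness, gagging, hemorrhoidal bleeding, bloating, rash, abdominal pain, syncope, tinnitus, chest burning, chills and flu-like symptoms. That is 14.

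**Step 2: follow typical non-serious events through the sections** (retained capsules, perforations and qualifying device deficiencies set aside).

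| Non-serious event | 8.5 and 11.1 | 11.0 list | 11.3 / 11.11 | 11.10 as worded |
|---|---|---|---|---|
| Not on the 11.10 list, unrelated to any procedure | captured | not listed | not an ADE; AE row applies | not exempt |
| On the list, caused by CCE, CTC or colonoscopy | captured | listed | reportable as ADE | not reportable |
| On the list, caused by preparation | captured | not clear | not clear | not reportable |
| On the list, Impossible to Determine | captured | not clear | not clear | not reportable |
| Not on the list, procedure-related | captured | listed | reportable as ADE | not exempt |

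Only the last row gets the same answer everywhere. The first row conflicts however 11.10 is read. The second conflicts only if 11.10 is applied as worded. The third is unclear because preparation is not one of the three types in 11.8, while Appendix A includes it among the CCE procedure instructions.

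**Step 3: can timing separate preparation from procedure?** Appendices A1, B1 and C1 put a preparation before CCE, CTC and colonoscopy alike, and 11.10 gives no end to the period after preparation. Timing therefore does not distinguish the two causes.

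**Step 4: could any loss differ by arm?**

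- *CCE versus CTC.* In Appendix A1 the boosts and the suppository come after capsule ingestion. In Appendix B1 the last agent is taken at 8pm the evening before. Procedure symptoms differ too. Section 6.1 ties bloating and mild pain to CTC. For the same 50-subject study, Table 1 gives mild abdominal pain in 10 patients with CTC, and difficulty swallowing the capsule in 2 as a minor complication of CCE. Bloating and abdominal pain are on the exempt list; difficulty swallowing is not. Unequal loss is therefore possible.
- *Colonoscopy.* Appendix C gives both arms the same preparation and procedure instructions. Listed symptoms caused by colonoscopy may be lost, but nothing shows that the loss would differ.

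**Step 5: carry this to 9.4.**

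- *Any AE:* the count depends on the section followed, on either reading of 11.10.
- *SAE:* not affected, since 11.0 collects SAEs and 11.10 excludes them from the exemption.
- *CCE/CTC-related AE:* open to unequal loss if 11.10 is applied as worded.
- *Colonoscopy-related AE:* possible under-count, with no unequal loss shown.

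**The case against.** The strongest reply is that 11.10 plainly means preparation effects. The amendment log gives the sponsor's reason for no longer collecting preparation AEs: procedure and device AEs matter more. 11.0 puts procedure-related AEs first, 11.11 has a row for device-related events, and the definition of Related in 11.8 already excludes reactions that other therapy reasonably explains. This is a fair reading and may well be the intended one. But 11.10 neither states that limit nor points to 11.8, and a symptom that is never entered does not reach the 11.8 classification. The closing sentence of 11.10 narrows the exemption by treatment needed, which is not a test of cause. The narrow reading also leaves the conflict between 8.5/11.1 and 11.0 in place.

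It can also be said that 11.0 is simply the outlier and never says its list is exclusive. That is right as far as it goes, and it makes the repair of 11.0 short.

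Three stronger inferences are tempting, and the documents do not support them.

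- A reader might infer that all the non-SAE comparisons are biased. For colonoscopy-related AEs the preparation is common to both arms. For unlisted, unrelated AEs randomization should balance occurrence, so leaving them out changes what is counted without favouring an arm.
- A reader might use the Table 1 pain counts to size or sign the bias. Those events were attributed to CTC, the fraction a site would drop under 11.10 is unknown, and the rates are not split between preparation and procedure.
- A reader might cross listed/unlisted with related/unrelated and report a proportion of conflicting classes. 11.8 has three relationship categories, so such a count is incomplete.

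**Conclusion.** The point holds as a contradiction in the current text; it does not rest on the amendment log. It has two parts. First, 8.5 and 11.1 (and 8.0 for the telephone calls) disagree with 11.0 on unrelated non-serious AEs. Second, the 11.10 exemption of 14 symptoms, as worded, overrides requirements in 11.0, 11.3 and 11.11 for procedure-caused events.

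The first part needs no choice between readings and leaves the any-AE comparison without a fixed definition. The second rests on the assumption that sites apply 11.10 literally; on the narrower reading the CCE/CTC-related and colonoscopy-related comparisons are not touched by it. Possible unequal loss is confined to the CCE/CTC-related comparison and to the share of the any-AE count made up of the same listed symptoms. Neither the direction nor the size of any bias can be derived from the documents. The SAE comparison, the primary endpoint and the accuracy endpoints are unaffected. The wording should be corrected, but the trial's main conclusion is not at risk from it.

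**What to change.** 1. Reconcile 8.5, 11.0, 11.1 and 11.10, with 8.0 in step, to a single capture rule applied identically in both arms over the window already stated.
2. Limit the 11.10 exemption to listed symptoms that the investigator attributes to bowel preparation, boosts included. Listed symptoms judged Related or Impossible to Determine for CCE, CTC or colonoscopy under 11.8 are then recorded as AEs.
3. State in 9.4 which AEs each of the four comparisons counts, including how Impossible to Determine is handled.

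This keeps the sponsor's decision not to collect preparation AEs. The cost is revised wording and some additional non-serious AE entries. There is also a real drawback: the trial is open label (8.10.3), so the attribution that decides whether a listed symptom is recorded is made by investigators who know the arm, and that judgement could itself differ between arms.

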### 11.11 Adverse Event Reporting

Please refer to the table below for a list of the minimum AE reporting requirements for investigators. If local regulations or IRB require faster reporting, then the investigator will adhere to those requirements. Reporting of all safety events to the Sponsor will be completed through Investigator submission of the AE eCRF in the remote data capture (RDC) system. In case of emergency only for SAEs and SADEs, the Principal Clinical Research Specialist or medical monitor may be contacted by phone; this will not serve as a substitute for proper reporting in RDC.

#### Investigator AE Reporting Requirements

Type	Report to	Reporting Timeframe (from time of learning of event)
Adverse Event (AE)	IRB/EC	Per IRB reporting requirements
	Sponsor	Within 10 working days
Serious Adverse Event (SAE)	Sponsor	Within 10 working days
	IRB/EC	Per IRB reporting requirements
Adverse Device Effect (ADE),	Sponsor	Within 10 working days
	IRB/EC	Per IRB reporting requirements

Serious Adverse Device Effect (SADE) and Unanticipated Serious Adverse Device Effect (USADE)		
Device Deficiency	Sponsor (technical support)	Within 10 working days
	IRB/EC	If SAE occurs due to the device deficiency, within 10 days and per IRB reporting requirements
Device Related AE/SAE	Sponsor	Within 10 days

All events will be reviewed by Medtronic safety officer or designee to determine any reporting obligations to the IRB.

## 12.0 Device Deficiencies

A device deficiency is an inadequacy of an investigational medical device related to its identity, quality, durability, reliability, safety, or performance. This may include malfunctions, misuse, or use error and inadequate labeling.

PillCam® COLON 2 Capsule endoscopy system device deficiencies will be documented on the appropriate device deficiency eCRF, and the device should be returned to Medtronic for analysis, if possible. Instructions for returning the investigational device will be provided. Device deficiencies should also be documented in the subject's medical record.

Device deficiencies are not to be reported as AEs. However, if there is an AE that results from a device deficiency, that specific event would be recorded on the appropriate eCRF.

## 13.0 Ethics and Compliance

### 13.1 Statement of Compliance

This clinical investigation will be conducted in accordance with the protocol and ethical principles that have their origin in the Declaration of Helsinki. The study will be conducted in compliance with the protocol, GCP and applicable regulatory requirements (1CFR 11, 21 CFR 50, 21 CFR 54, 21 CFR 56, 21 CFR 803, 21 CFR 812).

This may include an inspection by Medtronic representatives and/or Regulatory Authority representatives at any time. The investigator must agree to the inspection of study-related records by the Regulatory Authority/Medtronic representatives, and must allow direct access to source documents to the Regulatory Authority/Medtronic representatives. Regulatory Authority approvals/authorizations/notifications, where required, will also be in place and fully documented prior to study start.

### **13.2 Protocol Compliance**

No changes to the protocol will be permitted without the written approval from Medtronic and the IRB. The investigator must notify Medtronic and the reviewing IRB of any deviation from the Investigational Plan when specific to the protection of the life or physical well-being of a subject in an emergency. Such notice must be given as soon as possible, but in no event later than 5 working days after the emergency has occurred. Except in such an emergency, prior written approval by Medtronic is required for changes in or deviations from the Plan. If these changes or deviations affect the scientific soundness of the Plan or the rights, safety, or welfare of human subjects the IRB will also be notified. All other deviations will be reported per the site's IRB deviation policy. Should any deviations from the Investigational Plan occur, these will be reviewed by Medtronic for their clinical significance. If the event is performed without written approval from all parties, the investigator may be terminated from the study.

### **13.3 Institutional Review Board (IRB)**

Documented approval from the appropriate Institutional Review Board (IRB) will be obtained for all participating centers prior to study start, according to ICH GCP, local laws, regulations, and organization. When necessary, an extension, amendment, or renewal of the IRB approval must be obtained. The IRB must supply to the sponsor a list of the IRB membership and a statement to confirm that the IRB is organized and operates according to GCP and applicable laws and regulations.

### **13.4 Medical Monitor**

The Sponsor will utilize a Medtronic Medical Monitor to provide a medical review and adjudication in case requested by the safety officer or clinical study manager. Upon request by the safety officer or clinical study manager, the Medical Monitor will adjudicate relevant AEs in the Oracle RDC system (adjudication CRF). The Medical Monitor will not be affiliated with an investigative center.

During the review of AEs, the Medical Monitor will not be blinded to the randomized assignment or investigational site.

### **13.5 Subject Informed Consent**

A core information and consent form will be provided. Prior to the beginning of the trial, the investigator must have the IRB written approval/favorable opinion of the written ICF and any other written information to be provided to subjects. The written approval of the IRB together with the approved subject information/ICFs must be filed in the study files.

The process of obtaining informed consent must be in accordance with applicable regulatory requirement(s), and must adhere to GCP and to the ethical principles originating in the Declaration of Helsinki. Written informed consent must be obtained before any study specific procedure takes place. Participation in the trial and date of informed consent given by the subject should be documented appropriately in the subject files.

### 13.6 Insurance

Given Imaging Ltd, is a wholly owned subsidiary of Medtronic, which as the parent company of such entity maintains appropriate clinical study liability insurance coverage as required under applicable laws and regulations and will comply with applicable local law and custom concerning specific insurance coverage. If required, a clinical study insurance statement/certificate will be provided to the IRB.

